**8. Study Design:**

a. Recruitment Methods

Potential subjects will be recruited at their preoperative office visit with their surgeon or, if applicable, during their inpatient stay prior to surgery. Informed consent will be obtained by the Spectrum Health Oncology Research staff. The potential subjects include all patients scheduled to undergo major oncologic surgery that meet all of the

inclusion criteria, and none of the exclusion criteria. There will be no payment to study subjects. We plan to enroll a total of 200 subjects, unless planned interim analyses determine otherwise.

b. Inclusion Criteria

- Subjects undergoing major oncologic surgery for standard of care purposes (to include, but not limited to: liver resections, radical cholecystectomy, pancreaticoduodenectomy (Whipple procedure), esophagectomy, gastrectomy, colectomy, and debulking with hyperthermic intraperitoneal chemotherapy, prostatectomies, nephrectomies, and partial nephrectomies)
- Male or female  $\geq$  18 years of age
- Subject agrees to participate in this study and provides informed consent

Exclusion Criteria

- Subjects with a history of hypercoagulopathy, deep vein thrombosis or pulmonary embolism
- Subjects that are on anticoagulation or antiplatelet medications at the time of surgery other than Aspirin
- Subjects with a history of TIA or Stroke
- Subjects with a history of atrial fibrillation
- Subjects with a known thrombus
- Baseline creatinine level greater than 2.83 mg/dL
- Subjects with known hypersensitivity to tranexamic acid
- Adults unable to provide informed consent
- Children
- Pregnant women
- Prisoners
- Non-English speaking subjects
- Any other medical condition including mental illness or substance abuse deemed by the investigator to be likely to interfere with a subject's ability to provide informed consent, cooperate and take part in this research study

c. Study Endpoints

The primary outcome measures will be operative blood loss and transfusion rates in subjects undergoing the eligible procedures. Secondary outcome measures will include cost of hospitalization, intensive care unit length of stay, and total hospital length of stay.

d. Procedures Involved in the Research

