The study design will be a randomized, double-blind, placebo-controlled trial. Following satisfaction of inclusion/exclusion criteria and enrollment into the study, designated pharmacy staff will be notified of the patient's enrollment and scheduled timing of surgery. Designated pharmacy staff will randomize the patient and assign the patient a unique study number. The subject will be randomized based on a predetermined algorithm by the pharmacy staff to receive preoperative intravenous tranexamic acid or preoperative intravenous isotonic electrolyte solution as placebo. The preparation will be indistinguishable by nursing, surgical, or anesthesia staff. The tranexamic acid group will receive a 1000 mg dose immediately preceding surgery, administered by the anesthesiologist. Both the tranexamic acid and placebo will be administered via intravenous piggyback over 15 minutes. Standard daily

laboratory measurements will continue unless clinical conditions necessitate more frequent monitoring. Transfusion will take place for hemoglobin levels < 7.0 g/dL or hemoglobin level < 10 g/dL with clinical symptoms indicating need for transfusion, per standard practice. Final decision on transfusion will be made according to the staff surgical oncologist's discretion.

Data to be recorded from operative records will include operative blood loss, operative time, amount of fluid received, and intraoperative transfusion requirements. Postoperative data including hemoglobin levels, transfusion requirements, surgical complications, thromboembolic events, length of ICU stay, length of hospital stay, and cost of inpatient stay. Subjects will be followed for 90 days postoperatively. Additionally, re-admission to the hospital during this time will also be recorded with associated complications.

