**f. Provisions to Monitor the Data for the Safety of Subjects**

Adverse events including thromboembolic events and development of acute renal failure will be monitored and recorded on a weekly basis by study personnel. In the event an increased number of unanticipated events occur, the study will be temporarily stopped pending review. Review of unblinded data will be performed by an independent clinician, pharmacist, and statistician to determine the need to discontinue or resume the study. If a significant increase in adverse events is noted in the treatment arm, the trial will be terminated. Decisions resulting from the review will be discussed with the primary investigator.

Interim reviews of unblinded data for statistically significant findings will be performed by an independent clinician, pharmacist, and statistician after every 50 subjects complete the study. Findings will be reviewed with the investigators, and decisions will be made as to whether or not the research study continues. These interim reviews and outcomes will be reported to the IRB.

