### **b. Statistical Methods**

Summary statistics will be calculated. Quantitative data will be expressed as the mean $\pm$ SEM and nominal data will be expressed as a percentage. Comparisons between groups for quantitative variables will be performed using the t-test. Nominal variables will be evaluated using the  $c^2$  test. Significance will be assessed at  $p<0.05$ .

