## **10. Risks to Subjects**

Tranexamic acid is an FDA approved medication. The safety of tranexamic acid has been demonstrated in a meta-analysis of the off-label use of tranexamic acid in the perioperative period. A theoretical risk of thromboembolic events exists, though no significant adverse outcomes have been reported with the proposed dosing schedule. Refer to Pfizer Physician Prescribing Information document for a listing of potential adverse effects.

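### Thromboembolism is recorded and monitored but is not a named outcome, and its only planned final analysis is a percentage per arm and a low-powered chi-square with no interval estimate (cheap improvement)

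*Combined protocol and SAP*

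**What the plan says.** All references are to the combined protocol and SAP.

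- **Outcomes (8.c).** "The primary outcome measures will be operative blood loss and transfusion rates in subjects undergoing the eligible procedures". The next sentence reads: "Secondary outcome measures will include cost of hospitalization, intensive care unit length of stay, and total hospital length of stay". Neither sentence names a harm.
- **The risk (10).** "A theoretical risk of thromboembolic events exists, though no significant adverse outcomes have been reported with the proposed dosing schedule". The exclusion criteria in 8.b point the same way: they remove patients with prior deep vein thrombosis or pulmonary embolism, hypercoagulopathy, TIA or stroke, atrial fibrillation, or known thrombus.
- **Data collection (8.d).** The postoperative data items include "surgical complications, thromboembolic events, length of ICU stay", and "Subjects will be followed for 90 days postoperatively".
- **Monitoring (8.f).** "Adverse events including thromboembolic events and development of acute renal failure will be monitored and recorded on a weekly basis by study personnel". The section also provides for a pause, for unblinded review by an independent clinician, pharmacist and statistician, and for termination if adverse events rise significantly in the treatment arm. No test or level is given for that criterion.
- **Analysis (9.b).** Nominal data are summarised as percentages. "Nominal variables will be evaluated using the" chi-square test, with significance at p<0.05. No confidence interval is planned for any variable.
- **Subjects analysed (8.g, 9.a).** A subject with a thrombotic event before dosing is complete is withdrawn. Those who choose to withdraw before completing dosing are left out of the analysis. The sample size counts only subjects who complete dosing.

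**The concern.** The trial is meant to inform use of an antifibrinolytic in cancer surgery. If bleeding falls, the reader will want to know what happened to thrombosis. The events will be in the database, but the plan does not make them an outcome, define them, or say how the difference between arms will be estimated. By default they come under a significance test on sparse counts. With 100 per arm, that test will probably be non-significant even if the true risk has doubled, and a p-value alone does not show how large an increase the data still allow. The benefit would then be reported as a planned result, and the harm as a pair of percentages and an uninformative p-value.

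**Working it through.** **Inputs from the documents.** 100 subjects per arm (9.a); chi-square at p<0.05 (9.b).

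**Assumptions.** The test is two-sided, since 9.b does not say. The control-arm thromboembolism rate appears nowhere in the documents, so 1% to 5% is used, with 10% as an extreme. The effect examined is a doubling. The documents state no power or sample size for thromboembolism, so there is no safety figure of the plan's own to reproduce.

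**1. Power for a doubling.** The test statistic is z = (a - b)/100 ÷ √[p̄(1 - p̄)(2/100)], where a and b are the event counts and p̄ = (a + b)/200. Exact power is the sum of the products of the two binomial probabilities over all count pairs with |z| > 1.96.

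| Control v treated | Exact power | Chance of a non-significant result |
|---|---|---|
| 1% v 2% | 6% | 94% |
| 2% v 4% | 11% | 89% |
| 3% v 6% | 15% | 85% |
| 4% v 8% | 21% | 79% |
| 5% v 10% | 27% | 73% |
| 10% v 20% | 52% | 48% |

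As a check, take the normal approximation at 3% v 6%. The null standard error is √(0.045 × 0.955 × 0.02) = 0.0293. The alternative standard error is √(0.03 × 0.97/100 + 0.06 × 0.94/100) = 0.0292. Power ≈ Φ[(0.03 - 1.96 × 0.0293)/0.0292] = Φ(-0.94) ≈ 17%, against 15% exact.

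The choice of test matters too. With the Yates correction or Fisher's test, 3% v 6% has about 9% power. At those rates the expected count is (3 + 6)/2 = 4.5 events per arm, below the usual minimum of 5 for a chi-square.

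A tripling is also poorly detected: 28% for 2% v 6% and 43% for 3% v 9%.

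**2. What the rule would report.** Suppose 3 placebo and 6 treated subjects have an event.

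- z = 0.03/0.0293 = 1.02, so p = 0.31.
- The Wilson limits are 1.03% to 8.45% for 3/100 and 2.78% to 12.48% for 6/100.
- Newcombe lower limit: 3 - √[(6 - 2.78)² + (8.45 - 3)²] = 3 - 6.3 = -3.3 points.
- Newcombe upper limit: 3 + √[(12.48 - 6)² + (3 - 1.03)²] = 3 + 6.8 = +9.8 points.

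The p-value says not significant. The interval says that an increase of nearly 10 points has not been excluded. Even equal counts, 3 v 3, leave -5.8 to +5.8 points and a risk ratio interval of 0.21 to 4.84.

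**3. How large an imbalance the rule needs.** With 3 placebo events, 9 treated events give z = 0.06/√(0.06 × 0.94 × 0.02) = 1.79, p = 0.07. It takes 10: z = 0.07/√(0.065 × 0.935 × 0.02) = 2.01, p = 0.045.

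**4. Size of trial for 80% power to detect a doubling (normal approximation).** 749 per arm at 3% v 6%, and 435 per arm at 5% v 10%. Enlarging this trial is not a realistic answer; changing what is reported is.

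**The case against.** The strongest reply is that the plan already looks after safety. Events are collected, subjects are followed for 90 days, and 8.f provides independent unblinded review with power to end the trial. Percentages per arm are also already planned in 9.b, so it would be wrong to say that no harm summary is foreseen. All of this stands. But monitoring decides whether the trial continues; it does not supply a final estimate. Its termination criterion rests on an undefined significant increase. A percentage in each arm without an interval does not show what the difference could be.

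Four stronger readings are tempting, and the documents do not support them.

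- *A non-significant result will be presented as proof of safety.* A reader might infer this, but no section says so. The remark in Section 5 about benefit without more thromboembolic events is background drawn from earlier literature.
- *The named outcomes can only show benefit.* Cost, ICU stay and hospital stay can worsen, and Section 11 links cost to complications. They do not measure thrombosis, however. The word include in the secondary-outcome sentence also leaves that list open.
- *Power is 15%.* That figure needs a 3% control rate, which is an assumption. The range must accompany it.
- *The test is almost sure to miss a real increase.* Power of 27% at 5% v 10% and 43% at 3% v 9% is low, but it is not negligible.

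It is also fair to say that no 200-subject trial can be powered for this harm. The point asks for no more subjects.

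**Conclusion.** The point holds as a cheap improvement. Thromboembolism is the risk the protocol itself names, yet 8.c does not make it an outcome, and the default analysis in 9.b is poorly suited to sparse events. For a doubling with 100 per arm, the uncorrected chi-square has about 6% to 27% power over assumed control rates of 1% to 5%, and only 52% at 10%. These figures rest on the assumed rates, a two-sided 0.05 level and full enrolment. The conclusion that a non-significant result would be uninformative about harm does not depend on any one rate in that range.

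The completer restriction in 8.g and 9.a is a lesser matter. It could drop early thrombotic events from the comparison, but few are likely because the infusion lasts 15 minutes (8.d).

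**What to change.** **8.c.** Add a named safety outcome: any thromboembolic event to day 90, with a definition of what counts and how it is ascertained. List acute renal failure separately; it is recorded under 8.f and is not in the data list of 8.d, so add it there with the same 90-day window.

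**9.b.** Exempt these outcomes from the p<0.05 rule. Report counts per arm and the risk difference with a 95% score or exact confidence interval, in all subjects who received any study drug. State that, for these outcomes, this is an exception to the completer rule of 8.g and 9.a. Add that the trial is not powered to exclude an increase in thromboembolic events.

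**Cost.** A wording amendment, plus one added item in the data list for renal failure; thromboembolic events are already collected. There are no extra subjects or visits. The downside is that the interval will be wide, so the trial's safety statement will be more cautious.

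### Preoperative hemoglobin is neither a listed data item nor a covariate; adjusting the transfusion analysis for it could add roughly 0 to 12 points of power, depending on assumptions

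*Combined protocol and SAP*

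**What the plan says.** Section 8.c makes operative blood loss and transfusion rate the primary outcomes. Section 8.d gives the transfusion rule: "Transfusion will take place for hemoglobin levels" below 7.0 g/dL, or below 10 g/dL when symptoms point to a need. It follows this with "Final decision on transfusion will be made according to the staff surgical oncologist's discretion".

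Section 8.d also lists the data. From the operative record: "Data to be recorded from operative records will include operative blood loss, operative time, amount of fluid received, and intraoperative transfusion requirements". Afterwards: "Postoperative data including hemoglobin levels, transfusion requirements, surgical complications, thromboembolic events", then lengths of stay and cost. Neither list names a preoperative hemoglobin, and no other section does.

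Two passages bear on whether a preoperative value would exist. Section 8.d says of the standard daily tests that "laboratory measurements will continue unless clinical conditions necessitate more frequent monitoring". Section 8.b excludes subjects by "Baseline creatinine level greater than 2.83 mg/dL", so some blood result is needed before entry.

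In Section 9.b, quantitative variables get a t-test, and "Nominal variables will be evaluated using the" introduces the chi-square test. No covariates appear. Section 9.a says that randomization will equalize the types of surgery across arms, but type of surgery is not in the analysis either. Section 9.a also gives 100 subjects per arm and an anticipated 15-20% reduction in transfusion. It gives no control rate and no power.

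**The concern.** The trigger is an absolute hemoglobin level. For the same blood loss, a subject who starts lower reaches it sooner, so starting hemoglobin is likely to predict transfusion. Eligibility runs from prostatectomy to debulking with hyperthermic intraperitoneal chemotherapy, so starting values may vary widely.

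If so, an unadjusted comparison leaves explainable variation in the noise. Without the value on file, the report also could not show whether the arms were comparable on it, or express postoperative hemoglobin as a change from baseline. The covariate has to be named in advance. Section 8.f plans unblinded reviews after every 50 subjects, and a covariate chosen after those begin would be hard to defend.

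**Working it through.** **Inputs from the documents.** 100 per arm (9.a); significance at 0.05 (9.b), taken as two-sided because sidedness is not stated; reduction of 15-20% (9.a), absolute or relative not stated.

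**Inputs assumed.** Control transfusion rate, and the prognostic strength of preoperative hemoglobin.

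**Step 1: the plan's own figure.** With n per arm and mean rate p̄ = (p1 + p2)/2,

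power = Φ{ [ |p1 − p2| − 1.96·√(2p̄(1−p̄)/n) ] / √([p1(1−p1) + p2(1−p2)]/n) }.

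For 25% vs 10% and n = 100: (0.150 − 1.96 × 0.0537)/0.0527 = 0.85, so power is 80%. The same formula solved for 80% power gives 100 per arm for 25% vs 10% and 97 for 60% vs 40%. For a 15-point drop from control rates of 30-60% it gives 121 to 173. The total of 200 therefore fits some readings but cannot be reproduced uniquely. At 100 per arm:

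- 15-point drop, control 20-60%: power 57-90%.
- 20-point drop, control 25-60%: power 81-98%.
- Relative reduction of 15-20%, control 20-50%: power 8-29%.

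**Step 2: effect of adjustment.** Outcome model: logit P(transfusion) = a + b·arm + g·(standardized preoperative hemoglobin), calibrated to hold the marginal rates, 10,000 simulated trials per cell. The unadjusted chi-square is compared with the likelihood-ratio test for arm adjusted for hemoglobin. The values g = 0.5, 0.8 and 1.3 are odds ratios of about 1.6, 2.2 and 3.7 per SD toward lower hemoglobin (e^g), or areas under the ROC curve (AUC) of about 0.63, 0.70 and 0.79.

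| Control vs treated | Unadjusted power, % | Gain, g = 0.5 | Gain, g = 0.8 | Gain, g = 1.3 |
|---|---|---|---|---|
| 25 vs 10 | 81-83 | 1.6 | 2.6 | 6.7 |
| 30 vs 15 | 72-73 | 1.8 | 4.6 | 9.4 |
| 40 vs 25 | 62-64 | 2.0 | 5.3 | 12.0 |
| 50 vs 35 | 58-59 | 1.5 | 4.7 | 11.2 |
| 30 vs 10 | 95-96 | 0.5 | 1.6 | 2.4 |
| 40 vs 20 | 87-88 | 1.4 | 3.4 | 6.8 |
| 50 vs 30 | 83 | 1.9 | 4.6 | 8.4 |

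Gains are in percentage points. On a relative reading (15% or 20% off a control rate of 30% or 50%), unadjusted power is 11-31% and the gain runs from −0.4 (simulation noise) to 6.6 points. With no true effect, the adjusted test rejects in 5.0-5.4% of trials.

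**Step 3: cross-check.** If hemoglobin explains a share R² of outcome variance, the effective size is about n/(1 − R²). For 40% vs 25%, the Step 1 formula gives 62.1% at n = 100, 66.7% at 100/0.9 = 111 and 71.9% at 100/0.8 = 125. Those are gains of 4.6 and 9.8 points, in line with the table.

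**Step 4: chance imbalance.** The 95% range for the difference in mean standardized hemoglobin is ±1.96·√(2/100) = ±0.28 SD. The resulting shift in risk difference is about 0.28 × g × mean of p(1−p). For a 25% rate and odds ratio 2: 0.28 × 0.693 × 0.173 = 3.4 points. For a 50% rate and odds ratio 4: 0.28 × 1.386 × 0.183 = 7.1 points. These are shifts at the edge of the 95% range, so most trials would see less.

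**The case against.** The strongest reply is that the plan is valid as written. Randomization protects the unadjusted chi-square, and the chance imbalance in Step 4 is already inside its 5% error rate. That stands. A reader might infer that the missing adjustment biases the primary result, but the documents do not support that.

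A reader might also say that the plan forfeits a definite 3 to 12 points of power. That band needs a 15-point absolute drop and a moderate to strong predictor. With a weak predictor, or a drop from 30% to 10%, the gain is about 0.5 to 2.4 points.

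Three further points stand in part:

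- **Strength of the link.** The surgeon has the final decision, the higher threshold also requires symptoms, and intraoperative transfusion can follow acute blood loss. Transfusion is therefore not a mechanical function of starting hemoglobin. This weakens the link without removing it, and the g = 0.5 column allows for it.
- **Recording.** The list in 8.d may not be exhaustive, so the text supports saying that the value is not listed, but not that it will go unrecorded.
- **Availability.** Creatinine is not a blood count, and the sentence on daily tests mentions no preoperative draw. That a preoperative hemoglobin will be in the chart is a reasonable inference, not a documented fact.

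Finally, the simulation adjusts for hemoglobin only. It does not measure what procedure group adds, and it says nothing about operative blood loss.

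**Conclusion.** The point holds as an efficiency gain worth making. Transfusion is guided by hemoglobin thresholds, yet starting hemoglobin is not a listed data item. The analysis adjusts neither for it nor for the type of surgery that randomization is meant to balance.

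At 100 per arm, adjusting for hemoglobin would add roughly 0 to 12 points of power for transfusion. This rests on assumed control rates of 25-50% (30% or 50% on the relative reading), on either reading of 15-20%, and on an assumed AUC of about 0.63 to 0.79. A stronger predictor would add more, but nothing in the documents supports assuming one. No scenario showed a material loss of power or inflation of type I error.

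**What to change.** In 8.d, add the last preoperative hemoglobin, taken from the chart, to the recorded data.

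In 9.b, prespecify the primary transfusion analysis as a logistic regression on arm, preoperative hemoglobin as a continuous variable, and a small number of predefined procedure groups matching those used in randomization. Report a standardized risk difference with its 95% CI. Keep the chi-square as a sensitivity analysis. Define the procedure groups in writing, since the eligible list is long and open-ended, and state how a missing hemoglobin will be handled.

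The cost is one extra abstracted value per subject, a missing-value rule, and a regression in place of a simple test. The groups must be few: at 25% vs 10% only about 25 + 10 = 35 subjects would be transfused, and many procedure terms would leave sparse cells. The change affects data collection and analysis only; the transfusion rule is untouched.

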**e. Data Management**

The study personnel will collect outcome data on a weekly basis. Data will be stored in a password-protected file for security. Pharmacy staff will keep a secure record of subjects randomized to the tranexamic acid and placebo arms respectively, which will be blinded from the study personnel.

**f. Provisions to Monitor the Data for the Safety of Subjects**

Adverse events including thromboembolic events and development of acute renal failure will be monitored and recorded on a weekly basis by study personnel. In the event an increased number of unanticipated events occur, the study will be temporarily stopped pending review. Review of unblinded data will be performed by an independent clinician, pharmacist, and statistician to determine the need to discontinue or resume the study. If a significant increase in adverse events is noted in the treatment arm, the trial will be terminated. Decisions resulting from the review will be discussed with the primary investigator.

Interim reviews of unblinded data for statistically significant findings will be performed by an independent clinician, pharmacist, and statistician after every 50 subjects complete the study. Findings will be reviewed with the investigators, and decisions will be made as to whether or not the research study continues. These interim reviews and outcomes will be reported to the IRB.

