## **9. Statistical Plan**

### **a. Sample Size Determination**

We anticipate a 15-20% reduction in transfusion rates in the tranexamic arm when compared with placebo treatment. A sample size of 200 total subjects, 100 in each arm of the study, will be required to obtain a statistically significant result with  $p <0.05$ . Randomization will ensure an equal number of respective surgeries between the treatment and placebo arms of the study. All subjects who consent to the trial who meet the above inclusion criteria and complete the proposed dosing regimen will be included in the sample size.

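### Unblinded reviews every 50 completers have no efficacy boundary and the two primary outcomes have no success rule; testing at p<0.05 each time gives about 12.6% type I error per outcome, not 5%

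*Combined protocol and SAP*

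**What the plan says.** Section 8f, on safety monitoring, has two paragraphs. The first concerns adverse events. It has its own trigger, its own unblinded review and its own rule: "If a significant increase in adverse events is noted in the treatment arm, the trial will be terminated". The second describes something scheduled by completers: "Interim reviews of unblinded data for statistically significant findings will be performed by an independent clinician, pharmacist, and statistician after every 50 subjects complete" their participation. It then says: "Findings will be reviewed with the investigators, and decisions will be made as to whether or not the research study continues". It names no outcome, threshold or boundary.

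Section 8a fixes enrolment at 200 "unless planned interim analyses determine otherwise", so these reviews can change the size of the trial.

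Section 8c states: "The primary outcome measures will be operative blood loss and transfusion rates in subjects undergoing the eligible procedures". No section says whether either outcome suffices, both are needed, or one is tested first.

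Section 9a builds the sample size on one of the two: "We anticipate a 15-20% reduction in transfusion rates in the tranexamic arm when compared with placebo treatment". It says that 200 subjects "will be required to obtain a statistically significant result with" p<0.05, and it makes no allowance for interim looks. Section 9b assigns the t-test to quantitative variables ("Nominal variables will be evaluated using the" chi-square test) and sets significance at p<0.05. It does not adjust that level for repeated looks or for two outcomes.

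**The concern.** A 5% level belongs to one test of one outcome. Here the accumulating data may be tested up to four times, on each of two primary outcomes, and a significant result can end the trial. Each extra opportunity adds false positives unless the threshold is made stricter to pay for it.

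Most of the added error would come early, so a chance finding at 50 or 100 subjects could both end the trial and become its reported result. The fault cannot be repaired later: a boundary, or an order of primaries, chosen after unblinded findings have been discussed with the investigators would not be credible.

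**Working it through.** **The plan's own figure.** The 200 in section 9a can be neither confirmed nor refuted, because power and control rate are not given and the reduction is not identified as absolute or relative. It does fit some inputs. The formula per arm is n = [1.96·√(2p̄q̄) + 0.842·√(p₁q₁ + p₂q₂)]² / d², with p̄ the mean of the two rates:

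- 25% vs 10%: [1.96·√0.28875 + 0.842·√0.2775]² / 0.15² ≈ 100 per arm at 80% power.
- 60% vs 40%: [1.96·√0.50 + 0.842·√0.48]² / 0.20² ≈ 97 per arm.

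I therefore take 80% as an assumed reference for power below. If the reduction is relative, power at 100 per arm is only 8-40% for control rates of 20-60%.

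**Inputs for the error rate**

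- Looks at 50, 100, 150 and a final analysis at 200 (8f, 8a): information fractions t = 0.25, 0.50, 0.75, 1.00.
- 100 per arm (9a), so 25 per arm per stage.
- p<0.05 (9a, 9b), applied at each look: assumed. Two-sided: assumed, since sidedness is not stated.
- Success declared at the first crossing: assumed.

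**One outcome, four looks.** With no treatment effect, Z_k = S_k/√t_k, where S_k is a sum of independent normal increments of variance 0.25, so corr(Z_j, Z_k) = √(t_j/t_k) for j<k. Numerical integration of P(any |Z_k| > 1.96) gives:

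| Completers | Cumulative type I error |
|---|---|
| 50 | 5.0% |
| 100 | 8.3% |
| 150 | 10.7% |
| 200 | 12.6% |

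- False benefit alone: 12.6/2 = 6.3%, against 2.5%.
- Share arising before 200: 10.7/12.6 = 85%.
- If completion means the 90-day follow-up of section 8d, about 3 months × 15 operations a month (section 7) = 45 further subjects could be enrolled by the 150 look, if every case enrols. Without that look (50, 100, 200 only) the error is 11.3%.

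**With the named tests.** Simulated t-test: 12.6%. Simulated chi-square test for transfusion, with a common rate assumed because none is given:

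| Common rate | Uncorrected, four looks | Uncorrected, final only | Continuity-corrected, four looks | Continuity-corrected, final only |
|---|---|---|---|---|
| 20% | 13.2% | 5.1% | 7.1% | 3.2% |
| 30% | 12.9% | 5.1% | 7.9% | 3.5% |
| 40% | 13.8% | 5.2% | 8.7% | 3.6% |
| 50% | 14.6% | 5.6% | 9.5% | 4.0% |

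Section 9b does not say which form applies. Both exceed 5% with four looks.

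**Two primaries, either sufficing.** If independent: 1 − (1 − 0.1262)² = 23.6%. A single look would give 1 − 0.95² = 9.75%. Simulation with correlated outcomes:

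| Correlation | Unadjusted looks | O'Brien-Fleming, no rule for two primaries |
|---|---|---|
| 0 | 23.7% | 9.8% |
| 0.5 | 22.0% | 9.1% |
| 0.7 | 20.3% | 8.4% |
| 0.9 | 17.2% | 7.1% |

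**Both required at the same look.** With neither outcome affected, the error is 0.8, 2.7, 4.7 and 7.9% at the same four correlations. It can approach 12.6% when one outcome is strongly affected and the other is not.

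**A boundary that restores 5%.** O'Brien-Fleming uses |Z_k| > 2.024/√t_k, that is 4.05, 2.86, 2.34 and 2.02, or nominal p of about 0.00005, 0.004, 0.019 and 0.043; total 5.0%. With the chi-square test the totals are 4.6-5.1% uncorrected and 3.2-3.5% corrected.

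**The case against.** The strongest reply is that these are safety reviews. They sit under a safety heading, name no outcome, and use the same three roles as the adverse-event review. Section 9b attaches p<0.05 to comparisons between groups, not to interim looks. If the reviews never test efficacy, the error stays at 5% per outcome. This stands as a limit on the 12.6%, which is conditional. It does not clear the plan: adverse events already have a separate rule, the second paragraph is not limited to them, and section 8a calls these looks interim analyses that can change enrolment.

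It can also be said that an independent statistician, discussion before any decision and reporting to the IRB are safeguards, and that 12.6% assumes mechanical stopping in either direction. That is fair as to certainty, but none of these safeguards sets a threshold.

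Third, the 17-24% is the least favourable of the open readings of the two primaries. True; the figures for requiring both are shown beside it, and they do not guarantee 5% either.

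Finally, the cost looks larger against unadjusted looks than against a single test. That is correct, and both comparisons are given with the remedy.

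**Conclusion.** The concern holds. The absence of a boundary and of a success rule is plain from the text. With p<0.05 as the only threshold and looks that can end the trial, following the plan as written does not secure the 5% level in section 9b.

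The size is conditional on efficacy being tested, two-sided p<0.05 at each of four looks, and success at the first crossing. It is then about 12.6% per outcome, or 7.1-9.5% with a continuity-corrected chi-square test at the assumed rates. It rises to about 17-24% if either primary suffices. A boundary alone would still leave about 7-10% in that case, so both gaps need closing. This must be fixed before the first unblinded review.

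**What to change.** In sections 8f and 9b:

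1. State whether the 50-completer reviews test efficacy. If they do not, say so and remove the reference to statistical significance.
2. If they do, specify a group-sequential boundary with overall two-sided error of 5%. One example is O'Brien-Fleming, with nominal p of about 0.00005, 0.004, 0.019 and 0.043 at 50, 100, 150 and 200 completers.
3. State one rule for the two primaries, for example a fixed sequence starting with transfusion (the outcome the sample size is built on), each tested against the same boundary. This gives 5.0% error when neither outcome is affected. When only the first is affected, false claims on the second are at most 1.8% if the trial stops at the first crossing, and up to about 5.0% if it continues and the second is tested later.
4. Leave adverse-event monitoring unchanged.

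Boundary type and order of outcomes are the sponsor's choice.

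**Cost.** Wording only, no extra subjects. At a drift of 1.96 + 0.84 = 2.80 (the assumed 80% power), power falls from 80.0% with a single look to 79.1%. Against four unadjusted looks it falls from 84.3% to 79.1%, about 5 points, but that extra power came from the inflated error. Early efficacy stopping becomes rarer: the chance of crossing is 0.4% by 50, 19% by 100 (55% unadjusted) and 54% by 150 (73% unadjusted). Under a fixed sequence, the second outcome cannot be claimed if the first fails.
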